## 2.1.1 Demographic and baseline characteristics

# Demographic characteristics

Demographic variables are age in years (quantitative and qualitative variables: <65, [65 - 75] and ≥75 years; <65 and ≥65 years), gender (Male, Female), childbearing potential (Yes, No; for females only), race (White/Caucasian, Black, Asian/Oriental, American Indian or Alaska Native, Native Hawaiian or Other Pacific Island, Other), ethnicity (Hispanic or Latino, Not Reported/Unknown).

Age is calculated in years as:

Age = (date of informed consent - date of birth +1) /365.25.

For patients in countries where date of birth is not collected, age in years is directly collected in the electronic case report form (e-CRF).

# History of type 2 diabetes

History of type 2 diabetes includes the duration of diabetes in years (quantitative and qualitative variables: <5, [5-10] and >10 years).

#### Alcohol/smoking habits

Alcohol habits (alcohol drinking frequency, number of alcoholic drinks on a typical day when drinking) and smoking habits (never smoked, quit smoking, currently smokes); if quit smoking, time since stopped in years) will be presented.

#### Hypercholesterolemia history

Hypercholesterolemia characteristics are:

• Duration of hypercholesterolemia (years)

Property of the Sanofi Group - strictly confidential

26-Apr-2017

Version number: Final

26-Apr-2017

- History of hypercholesterolemia before type 2 diabetes diagnosis and duration between the diagnosis of hypercholesterolemia and the diagnosis of diabetes for patients with hypercholesterolemia diagnosed before diabetes.
- History of LMT ever taken (e.g., statin, fibrates, bile acid sequestrant, cholesterol absorption inhibitor, nicotinic acid and derivatives, omega 3 fatty acid ≥1000mg/day, PCSK9 inhibitor, other)
- History of down titration of any statin due to tolerability issues
- History of change to any different statin due to tolerability issues
- Currently taking statin
  - o If currently taking statin, whether subject receives the maximum dose per the local prescribing information
  - If not currently taking statin, statin intolerance status
    - If intolerant to statin, number of statin(s) previously prescribed at a dose lower than maximum and not tolerated
  - Reasons for taking a lower dose (including no dose if statin intolerant) when subject did not receive the maximum dose will be presented overall and by category (statin intolerant and not statin intolerant but taking a dose lower than the maximum dose):
    - Experienced muscle symptoms and/or increase creatine phosphokinase while taking a higher dose
    - Has liver disease or experienced elevated liver functions test while taking a higher dose
    - Taking concomitant medications that have precautions/warnings with statins
    - Advanced age
    - Low body mass index
    - Concern for cognitive impairment or experienced cognitive adverse event(s) while taking a higher dose
    - Concern for worsening of diabetes
    - Regional practice/local prescribing information
    - Other

# Cardiovascular (CV) history and CV risk factors

The coronary heart disease (CHD), CHD risk equivalents, and additional CV risk factors will be based on items or combination of items pre-listed in the 'Cardiovascular History' e-CRF page (unless otherwise specified).

Coronary heart disease and CHD risk equivalents will be detailed as follows:

- CHD (regardless if it is ongoing or not)
  - Acute myocardial infarction
  - Silent myocardial infarction
  - o Unstable angina

- Coronary revascularization procedures
- o Other clinically significant CHD diagnosed by invasive or non-invasive testing
- CHD risk equivalents (regardless if it is ongoing or not)
  - o Peripheral arterial disease (PAD), as defined by the occurrence of one of the following criteria (a, b, or c) based on the e-CRF fields:
    - a) Intermittent claudication (linked to PAD) with 'Ongoing' ticked "Yes" TOGETHER WITH ankle-brachial index ≤0.90 in either leg at rest,
    - b) Intermittent claudication (linked to PAD) TOGETHER WITH either peripheral revascularization procedure (angioplasty, stenting) for PAD or peripheral revascularization surgery (arterial bypass) for PAD or both,
    - c) Critical limb ischemia TOGETHER WITH either thrombolysis for PAD or peripheral revascularization procedure (angioplasty, stenting) for PAD or peripheral revascularization surgery (arterial bypass) for PAD or any combination of the three.
  - o Ischemic stroke

The following additional CV risk factors will also be considered:

- Hypertension established on antihypertensive medication
- Current cigarette smoker (as per smoking status from 'Smoking Habits' e-CRF page)
- Age  $\geq$  45 years old for men,  $\geq$  55 years old for women (age derived as detailed above in the 'Demographic characteristics' subsection)
- Microalbuminuria
- Macroalbuminuria
- Pre-proliferative diabetic retinopathy
- proliferative diabetic retinopathy
- Family history of premature (before 55 years of age in male, 65 years in female, first degree relatives) CHD
- Low HDL-C (male <40 mg/dL [1.0 mmol/L] and female <50 mg/dL [1.3 mmol/L])
- Chronic kidney disease (CKD) as defined by  $15 \le$  estimated glomerular filtration rate (eGFR) < 60 mL/min/1.73 m^2 for 3 months or more, including the screening visit)

Presentation of each risk factor will include:

- The occurrence
- Duration (years) of hypertension, microalbuminuria, macroalbuminuria, diabetic preproliferative retinopathy, diabetic proliferative retinopathy, and CKD
- Disease/symptoms controlled (if ongoing risk factor) for history of hypertension, microalbuminuria, macroalbuminuria, diabetic pre–proliferative retinopathy, and diabetic proliferative retinopathy

In addition, as per protocol, clinical atherosclerotic cardiovascular disease (ASCVD) is defined by any of the following history of CV diseases:

- CHD (as defined above)
- Ischemic stroke
- PAD (as defined above)

A second definition of clinical ASCVD including transient ischemic attack (TIA), as per the 2013 AHA/ACC guideline, is any of the following history of CV disease:

- CHD (as defined above)
- Ischemic stroke
- TIA
- PAD (as defined above)

# Allergic medical history

Occurrence will be presented for each allergic medical history:

- Allergic rhinitis
- Chronic sinusitis
- Nasal polyps
- Asthma
- Drug allergy
- Food allergy
- Pollen allergy
- House dust allergy
- Hives
- Swelling (angioedema)
- Fainting episodes
- Rash
- Other allergic medical history

Occurrence will also be presented for family allergic history:

- Asthma
- Allergic rhinitis

Allergies to food/pollen/dust

# Other relevant medical/surgical history

Other relevant medical/surgical history will be coded using the version of Medical Dictionary for Regulatory Activities (MedDRA) currently in effect at Sanofi at the time of database lock.

# Vital signs

Vital signs at baseline are weight in kg (quantitative and qualitative variables: <50, [50-70[, [70-100[,  $\geq$ 100 kg), height in cm, body mass index (BMI) in kg/m^2 (quantitative and qualitative variables: <25, [25-30[,  $\geq$ 30 kg/m^2), sitting systolic/diastolic blood pressures (SBP/DBP mmHg), heart rate (HR bpm).

# Other baseline characteristics

- Female menopausal status:
  - o occurrence
  - for postmenopausal women, time since menopause (years), menopausal symptoms controlled status and type of hormone replacement therapy (estrogen only, estrogen and progesterone, no estrogen or progesterone)
    - The type of hormone replacement therapy will be obtained from concomitant treatments.
- Lipid efficacy parameters:
  - o Non-HDL-C, quantitative and by category: <100, [100 130[, [130 160[, [160 190[, [190 220[, >220 mg/dL (<2.59, [2.59 3.36[, [3.36 4.14[, [4.14 4.91[, [4.91 5.70[, ≥5.70 mmol/L)]
  - Calculated and measured LDL-C, quantitative and by category: <70, [70-100[, [100-130[, [130-160[, [160-190[,  $\ge 190 \text{ mg/dL}$  (<1.81, [1.81-2.59,[] [2.59-3.37[, [3.37-4.14[, [4.14-4.91[,  $\ge 4.91 \text{ mmol/L})$
  - $\circ$  Apo B, quantitative and by category:  $<80, \ge 80 \text{ mg/dL}$  ( $<0.8 \text{ g/L}, \ge 0.8 \text{ g/L}$ )
  - Lp(a), quantitative and by category: <30, [30 50[,  $\ge 50$  mg/dL (<0.3, [0.3 0.5[,  $\ge 0.5$  g/L); <30,  $\ge 30$  mg/dL (<0.3,  $\ge 0.3$  g/L)
  - HDL-C, quantitative and by category: <40,  $\ge40$  mg/dL (<1.04,  $\ge1.04$  mmol/L) for men /<50,  $\ge50$  mg/dL (<1.29,  $\ge1.29$  mmol/L) for women
  - Fasting TGs, quantitative and by category: <150, [150 200[,  $\ge 200 \text{ mg/dL}$  (<1.7, [1.7 2.3[,  $\ge 2.3 \text{ mmol/L}$ ); <150,  $\ge 150 \text{ mg/dL}$  (<1.7,  $\ge 1.7 \text{ mmol/L}$ )
  - o TGRL, quantitative and by category:  $< 30, \ge 30 \text{ mg/dL}$  ( $< 0.3, \ge 0.3 \text{ g/L}$ )
  - All other quantitative lipid efficacy parameters (Total-C, Apo A-1, Apo C-III, ratio Apo B/Apo A-1, ratio Total-C/HDL-C, ratio LDL-C/HDL-C, LDL particle number and size, VLDL, HDL, IDL particle number)
- Metabolic parameters:
  - o Glycated hemoglobin A1c (HbA1c), quantitative (%, mmol/mol) and by category: <7, [7 9[, ≥9 %; <7, ≥7 %; <8, ≥8 %; <9, ≥9 %

26-Apr-2017

Fasting plasma glucose (FPG), quantitative variable (mg/dL and mmol/L)

26-Apr-2017

Version number: Final

- Total and free PCSK9 levels as quantitative (ng/mL)
- eGFR, quantitative and by category: [15 30], [30 60], [60 90],  $\ge 90$  ml/min/1.73 m^2
- Albumin/creatinine ratio, quantitative and by category: < 30, [30 300[,  $\ge 300 \text{ mg/g}$  (< 3.39, [3.39 33.9[,  $\ge 33.9 \text{ mg/mmol})$ ;
- Diabetic kidney disease category defined below (cf. Appendix C) (7):
  - o Category 1: G1A1, G2A1
  - o Category 2: G1A2, G2A2, G3aA1
  - o Category 3: G1A3, G2A3, G3aA2, G3bA1
  - o Category 4: G3aA3, G3bA2, G3bA3, G4A1, G4A2
  - o Category 5: G4A3, G5A1, G5A2, G5A3

Any technical details related to computation, dates, and imputation for missing dates are described in Section 2.5.

#### 2.1.2 Prior or concomitant medications

All medications taken within 3 months before screening visit and until the end of the study are to be reported in one of the following specific e-CRF pages:

- Cardiovascular Drugs
- Lipid Modifying Therapy (Including Statin) and Nutraceutical Products that May Affect Lipids
- Other Drugs

All medications will be coded using the World Health Organization-Drug Dictionary (WHO-DD) using the version currently in effect at Sanofi at the time of database lock.

- Prior medications are those the patient used within 12 weeks prior to screening visit and prior to first dose of open-label alirocumab injection/first dose of usual care treatment for those prescribed another LMT if allocated to the usual care arm. For those allocated to the usual care arm and for whom no other LMT is prescribed, the pre-treatment period will end on the day before randomization. Prior medications can be discontinued before first administration or can be ongoing during treatment phase.
- Medications taken at baseline are those the patient started before or on the day of the first dose of open-label alirocumab injection/first dose of usual care treatment (for those prescribed another LMT in the usual care arm)/randomization (for those not prescribed another LMT in the usual care arm), and ongoing or ended on or after the day of the first dose of open-label alirocumab injection/first dose of usual care treatment (for those prescribed another LMT in the usual care arm)/randomization (for those not prescribed another LMT in the usual care arm).

- Concomitant medications are any treatments received by the patient from first dose of open-label alirocumab injection to the last dose of open-label treatment + 70 days (10 weeks). For patients randomized to usual care, this will be considered as 70 days after the last dose of usual care treatment has been administered, or Study Day 225, whichever comes first. For patients randomized to usual care arm without additional LMT prescribed, the "date of last dose of usual care" is defined as the date of the last on-site visit. A given medication can be classified both as a prior medication and as a concomitant medication. Concomitant medications do not include medications started during the post-treatment period (as defined in the observation period in Section 2.1.4).
- Post-treatment medications are those the patient took in the period running from the day after concomitant treatment period up to when the patient terminates the study.

Any technical details related to computation, dates, imputation for missing dates are described in Section 2.5.

# 2.1.3 Efficacy endpoints

Efficacy parameters include lipid parameters (i.e., measured LDL-C, calculated LDL-C, non-HDL-C, Apo B, Total-C, Lp(a), TGs, HDL-C, TGRL, LDL particle number and size, Apo A-1, Apo C-III, ratio Apo B/Apo A-1, ratio Total-C/HDL-C, ratio LDL-C/HDL-C, VLDL, HDL, IDL particle number). These parameters (except TGRL, ratio Total-C/HDL-C and ratio LDL-C/HDL-C) are provided by the Central Laboratory. Measured LDL-C is obtained via beta quantification method. Calculated LDL-C is obtained using the Friedewald formula (5). If TG values exceed 400 mg/dL (4.52 mmol/L) then the Central Laboratory will reflexively measure (via the beta quantification method) the LDL-C rather than calculating it. All measured LDL-C values provided by the Central Laboratory including those done in case of TG values exceeding 400 mg/dL (4.52 mmol/L) will not be used for the analysis of calculated LDL-C endpoints. TGRL is derived as defined below.

Unless otherwise specified, all lipid values (scheduled or unscheduled, fasting or not fasting) may be used to provide a value for the primary and secondary efficacy endpoints. All measurements scheduled or unscheduled, fasting or not fasting, will be assigned to analysis windows defined in Section 2.5.3 in order to provide an assessment for Week 4 to Week 24 time points. For TG, only fasting measurements will be used and measurements with missing fasting status will be excluded from the analyses.

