### 2.1.3.2.3 Other efficacy endpoints (ITT estimand)

- Percent change in calculated LDL-C from baseline to Weeks 12 and 24
- Percent change in Apo B, Total-C, Lp(a), TGs, HDL-C from baseline to Week 12
- Proportion of patients reaching measured LDL-C <50 mg/dL (1.30 mmol/L), <70 mg/dL (1.81 mmol/L) and <100 mg/dL (2.59 mmol/L) at Weeks 12 and 24
- Percent change in measured LDL-C according to baseline TGs of <median TG or ≥median TG at Weeks 12 and 24
- Proportion of patients reaching non-HDL-C <130 mg/dL (3.37 mmol/L), <100 mg/dL (2.59 mmol/L) and <80 mg/dL (2.07 mmol/L) at Weeks 12 and 24
- Percent change in TGs from baseline to Weeks 12 and 24 according to baseline TGs of <median TG or >median TG
- Percent change in LDL particle number from baseline to Week 12
- Percent change in LDL particle size from baseline to Weeks 12 and 24
- Percent change in VLDL, HDL and IDL particle number from baseline to Weeks 12 and 24
- Percent change in Apo A-1 and Apo C-III from baseline to Weeks 12 and 24

- 26-Apr-2017 Version number: Final
- Absolute change in TGRLs (non-HDL-C minus measured LDL-C if measured LDL-C not missing; non-HDL-C minus calculated LDL-C if measured LDL-C missing and calculated LDL-C not missing, using fasting samples first, or if fasting sample missing using nonfasting measurements) from baseline to Weeks 12 and 24
- Proportion of patients with 50% or greater reduction from baseline in measured LDL-C at Weeks 12 and 24.
- Proportion of patients reaching Apo B <80 mg/dL at Weeks 12 and 24.
- Absolute change in ratio Apo B/Apo A-1, Total-C/HDL-C and LDL-C/HDL-C from baseline to Weeks 12 and 24.

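### Calculated LDL-C has no fasting restriction, although it contains a TG value that the SAP accepts only from fasting samples

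*SAP*

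**What the plan says.** SAP 2.1.3 sets a default for lipids: "Unless otherwise specified, all lipid values (scheduled or unscheduled, fasting or not fasting) may be used to provide a value". It then makes one exception: "For TG, only fasting measurements will be used and measurements with missing fasting status will be excluded from the analyses". No exception is made for calculated LDL-C, which the same section obtains by the Friedewald formula. That section also limits when the calculation is used: "If TG values exceed 400 mg/dL (4.52 mmol/L) then the Central Laboratory will reflexively measure" LDL-C instead, and such measured values are kept out of the calculated LDL-C endpoints.

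Calculated LDL-C is used in three places:

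- SAP 2.1.3.2.3 lists it as an other efficacy endpoint: "Percent change in calculated LDL-C from baseline to Weeks 12 and 24".
- The list of subgroups of interest that follows SAP 2.4.4.1.3 includes baseline calculated LDL-C.
- SAP 2.4.5.1 defines safety subgroups by two consecutive calculated LDL-C results, at least 21 days apart, below 25 or below 15 mg/dL. The common rules in SAP 2.4.5 again assign measurements to windows whether or not the patient fasted.

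TGRL is treated with more care. SAP 2.1.3.2.3 falls back on calculated LDL-C only when measured LDL-C is missing, and ranks the samples: "using fasting samples first, or if fasting sample missing using nonfasting measurements". SAP 2.4.4.3 adds two sensitivity analyses, one using measured LDL-C only and one using fasting samples only.

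On collection, Protocol section 10 (Blood sampling) tells sites not to draw a non-fasting patient but to rebook.

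**The concern.** The SAP treats a TG value as unusable when the sample is non-fasting or its fasting status is unknown. It then accepts the same value inside calculated LDL-C. A post-meal rise in TG would appear there as a fall in LDL-C that did not happen.

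The window rule in SAP 2.5.3 adds a second inconsistency. It takes the value nearest the target day without regard to fasting status. If a window holds a fasting and a non-fasting draw and the non-fasting one is nearer, TG comes from one blood sample and calculated LDL-C from another, at what is reported as the same time point.

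Three results are at stake: the descriptive calculated LDL-C comparison, allocation to the baseline calculated LDL-C subgroups, and entry into the very-low-LDL-C safety subgroups.

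**Working it through.** The plan gives no figure to reproduce, so the check is algebraic.

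**Inputs from the documents.** Non-HDL-C is Total-C minus HDL-C (SAP 2.1.3.1). LDL-C is not calculated when TG is above 400 mg/dL (SAP 2.1.3). Screening TG is at least 150 mg/dL (Protocol 7.1).

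**Assumptions.** The documents do not write out the Friedewald formula; the usual form with TG/5 in mg/dL is assumed. The post-meal TG rise d is taken as 25 to 100 mg/dL, and the share f of non-fasting samples in an arm as 1% to 10%. The documents give neither d nor f.

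**Step 1, formula.** Calculated LDL-C = Total-C − HDL-C − TG/5 = non-HDL-C − TG/5. With non-HDL-C held fixed, a TG rise of d changes calculated LDL-C by −d/5.

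**Step 2, one sample.** For d = 25, 50 and 100 the changes are −5, −10 and −20 mg/dL. For three illustrative profiles (mg/dL, with the change relative to the fasting value):

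| Non-HDL-C | Fasting TG | Fasting calculated LDL-C | d = 25 | d = 50 | d = 100 |
|---|---|---|---|---|---|
| 100 | 150 | 100 − 30 = 70 | 65 (−7.1%) | 60 (−14.3%) | 50 (−28.6%) |
| 150 | 250 | 150 − 50 = 100 | 95 (−5.0%) | 90 (−10.0%) | 80 (−20.0%) |
| 190 | 300 | 190 − 60 = 130 | 125 (−3.8%) | 120 (−7.7%) | 110 (−15.4%) |

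**Step 3, direction.** A non-fasting post-baseline sample makes the percent change look more negative. A non-fasting baseline does the opposite: with a true value of 100 at both times and a baseline read as 90, the percent change is 100 × (100 − 90)/90 = +11.1% instead of 0.

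**Step 4, arm mean.** The shift in an arm's mean post-baseline value is −f × d/5. At f = 1% and d = 25 it is −0.01 × 5 = −0.05 mg/dL. At f = 10% and d = 100 it is −0.10 × 20 = −2.0 mg/dL.

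**Step 5, safety thresholds.** A sample reads below 25 mg/dL when its fasting value is under 25 + d/5, that is, under 30 (d = 25) to under 45 (d = 100). For the 15 mg/dL threshold the limits are 20 to 35. Two qualifying results are needed, so one non-fasting sample matters only if the other result also qualifies.

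**Step 6, TGRL fallback.** Non-HDL-C minus calculated LDL-C equals TG/5, so a fallback TGRL is TG rescaled. The 400 mg/dL rule caps it at 400/5 = 80 mg/dL.

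**The case against.** The strongest reply is that little depends on this. Calculated LDL-C is an other efficacy endpoint, and SAP 2.4.4.4 makes its p-values descriptive. Measured LDL-C, which does not contain TG, is a key secondary endpoint at the same Weeks 12 and 24 (SAP 2.1.3.2.1), so a TG-free comparator stands beside it. Non-fasting draws should be rare. Nothing in the documents suggests that they would be commoner in one arm; if both arms were affected alike, the shift would largely cancel in the comparison. All of this stands and limits the importance of the point. It does not explain why one rule applies to TG and another to a quantity computed from it. The SAP does provide for non-fasting values, so the rule for them should be coherent.

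A reader might go further and infer that the main TGRL result is compromised. The documents do not support that. TG enters TGRL arithmetically only through the fallback, and measured LDL-C is scheduled at every lipid visit (Protocol 1.2). Fasting samples come first. The first analysis in SAP 2.4.4.3 removes the fallback and the second removes non-fasting samples. Nor is the 30 mg/dL TGRL cut-point a useful yardstick. It is a baseline category only, and a screening TG of at least 150 gives TG/5 of at least 30, so a post-meal rise from there moves away from the cut-point.

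It is also tempting to include the LDL-C/HDL-C ratio, but the SAP does not say which LDL-C enters it.

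**Conclusion.** The inconsistency is real but minor, and it concerns calculated LDL-C. SAP 2.1.3 excludes TG from samples that are non-fasting or of unknown fasting status, yet admits those samples to calculated LDL-C with no fasting preference and no sensitivity analysis.

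Under the stated assumptions the error is 5 to 20 mg/dL too low per affected sample, and 0.05 to 2.0 mg/dL in an arm's mean. The direction follows from the formula. The size rests on the assumed TG/5 term, TG rise and non-fasting share; the number of affected samples cannot be derived from the documents.

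A reader might infer that the trial's main conclusions are exposed. They are not: the primary endpoint is Total-C minus HDL-C, and the key secondary LDL-C endpoints use measured LDL-C. A difference between arms is not shown either.

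**What to change.** In SAP 2.1.3, extend the TG fasting rule, including the exclusion of samples with missing fasting status, to the calculated LDL-C efficacy endpoint and to the baseline calculated LDL-C subgroup factor. At minimum, keep the present rule and add a fasting-only sensitivity analysis for calculated LDL-C, parallel to the one in SAP 2.4.4.3 for TGRL. In either case, state whether the rule also governs the subgroups below 25 and 15 mg/dL in SAP 2.4.5.1.

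For consistency, the TGRL fallback in SAP 2.1.3.2.3 could be limited to fasting samples, but this is optional because both TGRL sensitivity analyses already cover that route. Non-HDL-C and measured LDL-C keep the present rule.

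The cost is a few lines of SAP text, one data filter and a few more missing values. The MMRM in SAP 2.4.4.2.1 handles missing post-baseline values. For baseline, the lipid panel is also drawn at screening (Protocol 1.2), so an earlier fasting value should often be available when the Week 0 sample is excluded.

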### 2.1.3.1 Primary efficacy endpoint

The primary efficacy endpoint is the percent change in non-HDL-C from baseline (see definition of baseline in Section 2.1) to Week 24 in the intent-to-treat (ITT) population.

Non-HDL-C is defined as Total-C minus HDL-C.

The percent change is defined as: 100 x (non-HDL-C value at Week 24 - non-HDL-C value at baseline) / non-HDL-C value at baseline.

26-Apr-2017

